#### 2 INTRODUCTION

#### 2.1 Study Rationale

As the number of immunocompromised patients, both adult and pediatric, continues to increase, IFIs, including IA, play a significant role in the morbidity and mortality seen in this population. There continues to be a need for the development of effective treatment options, particularly in the pediatric population for whom there are limited clinical study data detailing the treatment of IA. Recent advances in the adult population include the approval of POS in the US, European Union, and other countries for the primary treatment of IA [E.U. Summary of Product Characteristics 2022] [U.S. Prescribing Information 2022]. These approvals were based upon the completion of a prospective, randomized, double-blind study that showed the safety and efficacy of POS IV and tablet for the treatment of IA in adolescents and adults [Maertens, J. A., et al 2021].

Invasive aspergillosis occurs in pediatric (and adult) populations that are immunocompromised due to various pathologic and other factors, eg, malignancy, solid organ transplant or HSCT, primary immunodeficiency. The incidence rates of IA in high -risk patients vary by disease type and, in some instances, by geography and the use of prophylactic agents.

In children, IA is associated with significant increases in hospital length of stay and high overall in hospital mortality rates. Analyses of data from several major US hospitals showed an overall incidence of IA among hospitalized immunocompromised children of 437/100,000 (0.4%) [Pana, Z. D., et al 2017], and mortality rates in children with IA between 18% and 37% [Burgos, A., et al 2008].

Despite this unmet medical need, IA infections in immunocompromised pediatric patients have been understudied. To date, pediatric IA treatment options have been extrapolated from IA adult studies and treatment options [Burgos, A., et al 2008]. Current guidelines [Patterson, T. F., et al 2016] for the management of IA in adult patients recommend voriconazole (VOR) for the primary treatment of invasive pulmonary aspergillosis, with posaconazole, isavuconazole, or lipid formulations of amphotericin B as alternative primary therapies[Douglas, A. P., et al 2021]. However, guidelines are limited given the paucity of prospective study data in the pediatric population.

A small number of studies have provided data regarding recent treatment choices for pediatric patients diagnosed with IA. A 2017 trial of VOR in pediatric participants with IA demonstrated that safety and efficacy outcomes were consistent with previous findings in adult patients [Martin, J. M., et al 2017]. In this 2017 trial, 31 children (14 with proven or probable infection) were enrolled and treated for IA for 6 to 12 weeks. After 6 to 12 weeks of VOR therapy, the global clinical response was 64%. AEs were common, with 30/31 (97%) participants reporting one or more AEs, and 16/31 (52%) of the AEs were considered related to study therapy. In this trial, an association between hepatic AEs and higher VOR exposures was noted, although due to the small sample size, data interpretation was limited. Overall, 48% of participants treated with VOR discontinued therapy early. These results indicate the need to identify alternate therapies for IA that are more efficacious and/or better tolerated.

POS is a highly active triazole with potential advantages in terms of tolerability and drug interactions. POS (IV, PFS, and tablet formulations) has been recently approved for use in children 2 to <18 years of age for the salvage treatment and the prophylaxis of IFIs. This approval was based on data from a prospective PK and safety study that evaluated POS IV and PFS in children 2 to 17 years of age who were at high risk of an invasive fungal infection [Groll, A. H., et al 2020].

The use of newer formulations of POS (PFS, tablet, and IV) provides higher POS concentrations in pediatric patients than the oral suspension formulation and supports the use of the IV formulation in pediatric patients who are unable to tolerate oral dosing. As the newer IV, tablet, and PFS formulations of POS achieve higher POS exposures, the newer formulations have the potential for improved clinical effectiveness.

As immunocompromised pediatric patients are at risk for IA, it is appropriate to study the efficacy and safety of POS IV and oral formulations (PFS and tablets) for the primary treatment of IA in children. This trial evaluates safety, efficacy, and PK of POS IV and oral formulations (PFS and tablets) in pediatric participants 2 to <18 years of age with IA.

# 2.2 Background

Refer to the IB and approved product labeling for detailed background information on posaconazole (MK-5592, POS).

### 2.2.1 Pharmaceutical and Therapeutic Background

POS is a broad-spectrum triazole antifungal compound approved for the prophylaxis and salvage treatment of IFIs in pediatric patients 2 to <18 years of age. POS is also approved for the primary treatment of IA as well as prophylaxis and salvage treatment of IFIs in adolescents and adults. The approved labeling of indications and patient populations vary by country. Currently approved POS formulations include an IV solution and 3 oral formulations (a pre-mixed liquid suspension, a powder for suspension to be mixed in a suspending vehicle, and a delayed-release tablet). The powder for suspension and the delayed-release gastric tablet formulations overcome limitations in the oral bioavailability of the oral suspension, allowing for once-daily dosing and, as such, are preferred oral formulations. The oral PFS formulation consists of the same delayed-release compound as the tablet in a formulation that allows for more flexible weight-based dosing. A Phase 1B trial [MK-5592-097 (P097)] has provided PK and safety data for use of the IV and PFS formulations, when given prophylactically to children at risk of IFI, that supported the approval of these formulations in patients 2 through 17 years of age.

# 2.2.2 Preclinical and Clinical Studies

Refer to the IB and approved POS labeling for detailed information on prior preclinical and clinical studies conducted with POS.

# 2.2.3 Ongoing Clinical Studies

There is 1 study ongoing, in addition to the current study, that is evaluating the use of POS in the pediatric population. In addition to this protocol, there is also another ongoing Phase 2 clinical study of POS evaluation in the treatment of invasive fungal infections in pediatric patients 0 to 2 years of age (P127).

# 2.3 Benefit/Risk Assessment

It cannot be guaranteed that participants in clinical studies will directly benefit from treatment during participation, as clinical studies are designed to provide information about the safety and effectiveness of an investigational medicine.

POS has been shown to be of benefit in the treatment of IA and other IFIs in controlled as well as uncontrolled studies and in salvage therapy studies using the IV, tablet, and oral suspension formulation in adults, and the IV and PFS formulation in pediatric participants [Walsh, T. J., et al 2007] [Lehrnbecher, T., et al 2010] [Maertens, J. A., et al 2021] [Groll, A. H., et al 2020]. In addition, literature reports of POS IV and tablet have indicated the benefit of the POS when used to treat mold infections, including IA, in high-risk patients [Conant, M. M., et al 2015] [Jeong, W., et al 2016]. The most common toxicities that have been reported with POS include gastrointestinal events (diarrhea, nausea, and vomiting), fever, headache, and cough. The following risks have been identified in patients treated with POS per product labeling: hypersensitivity, hepatic toxicity, QTc prolongation, and drug interactions. Refer to current POS (NOXAFILTM) product labeling for additional information. The safety and efficacy of POS in children <2 years of age has not been established. Current product labeling indicates approval in children 2 years of age and older and adults.

Additional details regarding specific benefits and risks for participants participating in this clinical trial may be found in the accompanying IB and informed consent documents.

# **3** HYPOTHESES, OBJECTIVES, AND ENDPOINTS

There are no hypotheses for this trial. The following objectives and endpoints will be evaluated in male and female pediatric participants aged 2 to <18 years with invasive aspergillosis (IA): time points at which each of the endpoints will be evaluated are presented in Section 9.1.
Objectives	Endpoints			
Primary				
• Objective: To evaluate the safety of POS (IV and oral formulations overall)	Treatment-related AEs			
Secondary				
• Objective: To evaluate the efficacy of POS (IV and oral formulations overall) in participants with possible, probable, or proven IA	• Global clinical response (partial or complete response)			
• Objective: To evaluate relapse in participants with possible, probable, or proven IA who have completed treatment with POS (IV and oral formulations overall) and achieved favorable global clinical response (complete or partial)	• Relapse of IA, defined as the re-emergence of clinical, radiographic, or other relevant abnormalities indicating IA			
• Objective: To characterize the PK of POS overall and by formulation	
 
Key PK parameters, consisting of Cavg, Cmin, Cmax, AUC, and Tmax, using sparse plasma concentration sampling (steady-state trough and peak)
 
Analysis of exposure-response (efficacy and safety) relationships
 
			
• Objective: To summarize the palatability and acceptability of POS powder for suspension (PFS) formulation	• Participants' categorical perception of the taste of the PFS formulation			
Tertiary/Exploratory				
• Objective: To evaluate all-cause mortality in participants treated with POS (IV and oral formulations overall)	• Deaths			

The timing of all assessments, including those not directly related to endpoints, is described elsewhere in the protocol (Sections 1.3, 8.2, 8.3, 8.4, 8.6, 9.1 and 9.4).

#### 4 STUDY DESIGN

#### 4.1 Overall Design

This is a nonrandomized, open-label, noncomparative, Phase 2, multi-site trial of POS IV and oral formulations in pediatric participants aged 2 to <18 years with IA, as defined by 2020 European Organization for Research and Treatment of Cancer/Mycoses Study Group (EORTC/MSG) consensus definitions [Donnelly, J. P., et al 2020]. Individuals who meet the criteria for possible, probable, or proven IA will be enrolled.

After a screening period of up to 14 days, participants will be allocated to receive open-label POS study treatment. All participants will initiate treatment with the POS IV formulation. After a minimum of 7 days on POS IV, and when the participant is considered clinically stable and able to take oral study treatment, per investigator judgment, participants may transition to oral study treatment with either the POS tablet formulation or the POS PFS formulation, based on their weight. The initial transition to POS oral formulation (either PFS or tablet) should occur no later than the Week 9 visit and must occur under medical supervision at the study site. After transitioning to one of the oral POS formulations, additional transitions between oral and IV formulations are permitted as clinically indicated.

The planned total duration of study treatment across all formulations is 6 to 12 weeks (42 to 84 days); the actual treatment duration for each participant will be based on the investigator's clinical judgment. Participants should complete all study visits regardless of when they complete study treatment. Doses and additional details of study treatment are provided in Section 6.1.

Safety, efficacy, and PK assessments will be conducted throughout the treatment period, and safety and efficacy assessments at the follow-up visits, 14 (+2) and 28 (+2) days after the last dose of study treatment and at Day 114 (+7 days), as specified in Section 1.3. All participants will be followed for survival through Day 114. The trial's objectives are stated in Section 3 and include safety (primary objective) as well as efficacy, PK, and palatability and acceptability (secondary objectives).

Participants will participate in the trial for up to approximately 128 days: up to 14 days of screening, up to 84 days of treatment, and approximately 30 days of follow-up after the 84-day planned treatment period.

Specific procedures to be performed during the study, as well as their prescribed times and associated visit windows, are outlined in the SoA in Section 1.3. Details of each procedure are provided in Section 8.

Approximately 30 participants will be enrolled to achieve at least 15 participants as characterized below in the FAS population (Section 9.5.1). Participants will be enrolled into the following age cohorts, which will enroll simultaneously:

- Age Cohort 1 (2 years to <12 years of age): approximately 20 participants enrolled to achieve at least 10 in the FAS population who transition to oral therapy (PFS or tablet) for at least 7 days after the end of IV treatment with POS.
- Age Cohort 2 (12 years to <18 years of age): approximately 10 participants enrolled to achieve at least 5 in the FAS population who transition to oral therapy (PFS or tablet) for at least 7 days after the end of IV treatment with POS.

For ongoing safety evaluations and to ensure safe study conduct, an independent, external DMC will be established. Specific details regarding the DMC will be described in the DMC charter.

# 4.2 Scientific Rationale for Study Design

As immunocompromised pediatric patients (aged <18 years of age) are at high risk for IA, newer treatments are needed for pediatric patient populations. POS IV and tablet formulations have been studied in adolescents and adults for the primary treatment of IA and have demonstrated efficacy and safety for this indication. Thus, it is reasonable to further study the safety and efficacy of POS IV, tablet, and PFS in the primary treatment of IA in the pediatric population (see Section 2.2.3).

# 4.2.1 Rationale for Endpoints

# 4.2.1.1 Efficacy Endpoints

Efficacy is not a primary endpoint in this study. The efficacy endpoint (secondary) is the proportion of participants with a diagnosis of possible, probable, or proven IA and a favorable global clinical response. This endpoint will be assessed by the investigator using the published definitions for defining responses to therapy and study outcomes in clinical trials of invasive fungal diseases [Segal, B. H., et al 2008] and as presented in Section 8.2.1. The assessment of the efficacy endpoint in pediatric participants with a classification of possible, probable, or proven IA is similar to the efficacy population analyzed in the adult study (MK-5592-069 P069) of IA. Additional efficacy endpoints are:

- An assessment of relapse of IA in participants with possible, probable, or proven IA who have achieved a favorable global clinical response after completion of study treatment (secondary endpoint, Section 9.4.1.1).
- An evaluation of all-cause mortality at Study Day 42 (exploratory endpoint, Section 9.4.1.3). All-cause mortality at Study Day 42 as an efficacy endpoint has been considered an accepted endpoint for recent clinical studies of IA in adults and adolescents[Martin, J. M., et al 2017]. All-cause mortality will also be evaluated at Study Day 114.

# 4.2.1.2 Safety Endpoints

The safety of POS in this pediatric population will be primarily assessed by the evaluation of treatment-related AEs. Other assessments may include evaluation of all AEs (regardless of causality), as well as laboratory and ECG safety parameters.

## 4.2.1.3 Pharmacokinetic Endpoints

Key PK parameters will be calculated from sparse plasma concentration data based on previously developed population PK models for each formulation in pediatric participants.

Exposure/response assessments will also be conducted, including an exploration of the relationship between PK parameters and measures of efficacy and safety.

## 4.2.1.4 Additional Endpoints

Palatability and acceptability parameters for the POS PFS formulation will be assessed in all participants who receive this formulation (refer to Section 8.3.5 for further details of the palatability assessment).

## 4.2.2 Rationale for the Use of Comparator/Placebo

This study is designed to obtain efficacy and safety information regarding the use of POS IV and oral formulations as primary treatment of IA in children  $\geq 2$  and < 18 years of age. To obtain as much experience as possible with POS treatment in this trial, given the limited participant population, no comparator will be assessed. POS has previously been demonstrated to be efficacious in the primary treatment of IA in a double-blind comparative study of POS IV and tablet compared with VOR IV and oral formulations when given to adults and adolescents [Maertens, J. A., et al 2021].

Given the high rate of mortality of IA among untreated patients, the use of a placebo treatment arm has not been considered.

#### 4.3 Justification for Dose

#### 4.3.1 Starting Dose for This Study

All randomized participants will begin study dosing with the IV formulation of POS. The dose of 6 mg/kg/day for the IV formulation was chosen for this study based on the results of the Phase 1B PK and safety study of POS in children and adolescents (P097) as well as the approved dosing of POS IV for children 2 years of age and older. Participants will receive POS IV at a dose of 6 mg/kg/day BID on Day 1 and QD thereafter.

After at least 7 days and when clinically appropriate, participants can be switched to an oral formulation. Participants weighing  $\leq$ 40 kg will transition to the PFS formulation. The dosing for the PFS formulation, shown in Table 1, reflects the approved pediatric weight-based dosing of this formulation and reflects the approved labeled dosing of this formulation. Weight-band dosing is expected to provide POS exposures similar to that previously

specified in the protocol before implementation of this amendment. Participants weighing >40 kg will transition to the tablet at a dose of 300 mg. The choice of 40 kg as the weight to transition to a 300-mg tablet dose aligns with the pediatric dosing of the tablet in approved product labeling for POS tablet. The dosing of the tablet also reflects the approved dosing of POS tablet as shown in product labeling for the treatment of IA.

Weight (kg)	PFS Dose (volume)
10-<12 kg	90 mg (3 mL)
12-<17 kg	120 mg (4 mL)
17-<21 kg	150 mg (5 mL)
21-<26 kg	180 mg (6 mL)
26-<36 kg	210 mg (7 mL)
36-40 kg	240 mg (8 mL)
PFS= powder for delayed release oral suspension	

Table 1 Dosing of the PFS

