#### Number of Participants:

Approximately 30 participants will be enrolled in the trial to achieve at least 15 participants in the Full Analysis Set (FAS) population (defined in Section 9.5.1) as characterized below.

Participants will be enrolled into the following age cohorts, which will enroll simultaneously:

• Age Cohort 1 (aged 2 to <12 years): approximately 20 participants enrolled to achieve at least 10 in the FAS population who transition to oral therapy (PFS or tablet) for at least 7 days after the end of IV treatment with POS.

• Age Cohort 2 (aged 12 years to <18 years): approximately 10 participants enrolled to achieve at least 5 in the FAS population who transition to oral therapy (PFS or tablet) for at least 7 days after the end of IV treatment with POS.

Intervention							
Groups	Treatment Name	Drug	Dose Strength	Dose Frequency	Route of Admin- istration	Regimen/ Treatment Period b	Use
	Posaconazole	Posaconazole IV a	18 mg/mL	QD, except BID on Day 1	IV infusion	Day 1: BID 6 mg/kg Day 2 through end of IV dosing: QD 6 mg/kg	duct
	Posaconazole	If weight ≤40 kg: Posaconazole PFS	30 mg/mL	QD	Oral	Days 8 – 84: weight-band dosing, see Table 1.	Test Proc
	Posaconazole	If weight >40 kg: Posaconazole Tablet	100 mg	QD	Oral	Days 8 – 84: 300 mg	
	Abbreviations: suspension; a: There is a ma BID, with u b: The posacon formulation indicated. Other current follows: MK-	BID = twice dail QD = once dail uximum dose of p to 300 mg IV azole IV formula s (PFS or tablet) or former na 5592; Noxaf	ly; IV = intravendy. 300 mg per admi in each dose. ation is to be adm may be administ ame(s) or alia fil; SCH 5659	ous; PFS = po nistration; on hinistered for a tered beginnin as(es) for s 92.	wder for de Day 1 only 1 minimum g on Day 8 tudy inte	elayed-release of , dosing frequen of 7 days; oral as clinically ervention(s)	al cy is are as
Total Number	There will be	a single inte	rvention arm				

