# 4.3.2 Maximum Dose/Exposure for This Study

For a given participant, the maximum planned dose of POS is 300 mg per administration (administered BID on Day 1 and QD on subsequent days for a maximum of 84 days). Participants who weigh >40 kg will receive the maximum planned dose of 300 mg. The maximum total daily dosing established for this study reflects the approved dose for POS solid oral tablet and POS IV solution formulations, which is 300 mg BID on Day 1 followed by 300 mg QD.

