# Table 3Study Treatments

Arm Name	Arm Type	Intervention Name	Intervention Type	Dose Formu- lation	Unit Dose Strength(s)	Dosage Level(s)	Route of Adminis- tration	Regimen/ Treatment Period	Use	IMP or NIMP/AxMP	Sourcing
Posaconazole	Experi- mental	IV	Drug	Vial	18 mg/mL	6 mg/kg Doses are not to exceed 300 mg per administration	IV Infusion	Day 1: BID Day 2 through end of IV dosing: QD	Test Product	IMP	Centrally sourced with the ability to source locally if required
Posaconazole	Experi- mental	Powder for suspension (PFS)	Drug	Powder for Suspension	30 mg/mL	Dosing based on weight-band. To be administered to participants ≤40 kg	Oral	Days 8 – 84: QD	Test Product	IMP	Centrally sourced with the ability to source locally if required
Posaconazole	Experi- mental	Tablet	Drug	Tablet	100 mg	300 mg To be administered to participants >40 kg	Oral	Days 8 – 84: QD	Test Product	IMP	Centrally sourced with the ability to source locally if required

Abbreviations: AxMP Auxiliary Medical Product, EEA=European Economic Area, IMP= Investigational medical product, NIMP=non-investigational medical product, QD= Once daily

The classification of Investigational Medicinal Product (IMP) and Non-Investigational Medicinal Product (NIMP) in this table is based on guidance issued by the European Commission and applies to countries in the European Economic Area (EEA). Country differences with respect to the definition/classification of IMP/NIMP may exist. In these circumstances, local legislation is followed.

All supplies indicated in Table 3 will be provided per the "Sourcing" column depending upon local country operational requirements. If local sourcing, every attempt should be made to source these supplies from a single lot/batch number where possible (eg, not applicable in the case where multiple lots or batches may be required due to the length of the study, etc).

Refer to Section 8.1.8 for details regarding administration of the study intervention.

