# 8.1.8 Study Intervention Administration

IV infusions should be administered via a central line at approximately the same time each day. On the first 24 hours of IV dosing, there is a loading period during which 2 doses are given, separated by 12 hours. Subsequently, a single dose is given once daily. For the third dose, the dose should be timed to be given approximately 24 hours after the initial loading dose (ie, approximately 12 hours after the second loading dose). All subsequent IV doses should be administered approximately 24 hours apart. If for any reason the timing of the medication needs to be adjusted after the first dose, the dose time may be adjusted by  $\pm 3$  hours.

Doses of POS PFS and tablets will be administered every 24 hours during the oral treatment period, without regard to timing of food intake. If for any reason, the timing of the medication needs to be adjusted after the first dose, the dose time may be adjusted by  $\pm$  3 hours. Participants who vomit within 30 minutes of POS PFS or tablet administration should be given a replacement dose as soon as the participant is able to take the new dose. Repeated episodes of vomiting should be recorded on the AE electronic case report form (eCRF) and the Study Medication eCRF.

If the dosing of study treatment is delayed, the dose should be administered as soon as possible. If it is more than 6 hours since the missed dose, the missed dose should be skipped, and the next dose should be administered at the regularly scheduled time. Any missed doses should be properly documented in the participant's eCRF and source documentation.

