# 8.5 Treatment of Overdose

In this study, an overdose is any dose higher than the protocol-specified dose as provided in Section 6.1.

Decisions regarding dose interruptions or modifications will be made by the investigator in consultation with the Sponsor's Clinical Director based on the clinical evaluation of the participant.

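### Section 4.3.1 gives the Day 1 IV dose in a per-day unit, while the synopsis and Table 3 give it per dose; read literally, the Day 1 totals differ twofold up to 50 kg

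*Combined protocol and SAP*

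**What the plan says.** Section 4.3.1 uses a per-day unit twice. The rationale sentence reads "The dose of 6 mg/kg/day for the IV formulation was chosen for this study", and the instruction that follows reads "Participants will receive POS IV at a dose of 6 mg/kg/day BID on Day 1 and QD thereafter".

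The other places that describe IV dosing do not use that unit:

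- The synopsis, in the intervention table: "Day 1: BID 6 mg/kg Day 2 through end of IV dosing: QD 6 mg/kg".
- Section 6.1, Table 3, dosage level: "6 mg/kg Doses are not to exceed 300 mg per administration". The regimen column adds "Day 1: BID Day 2 through end of IV dosing: QD".
- Section 4.3.2: "the maximum planned dose of POS is 300 mg per administration (administered BID on Day 1 and QD on subsequent days".
- Section 8.1.8, describing how IV treatment starts: "there is a loading period during which 2 doses are given, separated by 12 hours. Subsequently, a single dose is given once daily".

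On which section governs, the protocol points in two directions. Section 4.1 refers the reader to Section 6.1 for doses. Section 8.9.2.2 refers the reader to Section 4.3 for dosing selection and to Section 6.2 for preparation. Section 6.2.1 describes Section 4.3 as rationale, says which body weight to use for the IV dose, gives no mg/kg figure, and leaves IV preparation to the Pharmacy Manual.

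**The concern.** A mg/kg/day unit combined with BID ordinarily means a daily total divided in two. A mg/kg dosage level combined with BID ordinarily means that amount at each administration. The two conventions give different Day 1 doses for the same child, and nothing in the protocol says that the per-day wording in Section 4.3.1 is meant per infusion.

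The per-day unit causes no difficulty from Day 2, because one 6 mg/kg infusion a day is 6 mg/kg/day. The conflict arises only where the same unit is attached to two infusions on Day 1.

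At stake are the first IV doses given to children aged 2 years and over with invasive aspergillosis. If any site worked from Section 4.3.1 and others from Table 3, Day 1 dosing would differ between sites. The percent-compliance formula in Section 9.11 would not show it, because a day with at least one infusion counts as a day on therapy whatever the amount. Under Section 8.6 the Day 1 PK sample is predose and the next is at Week 1, so Day 1 exposure is not sampled directly.

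**Working it through.** **Inputs**

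- Dose figure: 6 mg/kg (Sections 1.1, 4.3.1 and 6.1).
- Infusions: two on Day 1, one a day afterwards (Sections 1.1, 6.1 and 8.1.8).
- Cap: 300 mg per administration (Sections 4.3.2 and 6.1).
- Minimum weight at entry: 10 kg (Section 5.1, criterion 7).
- The weights tabulated above 10 kg are illustrative; the protocol sets no upper limit.

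**Formulas**, for body weight w in kg:

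- Synopsis and Table 3, read per infusion: Day 1 total A = 2 × min(6w, 300).
- Section 4.3.1, read literally as a divided daily total: Day 1 total B = 2 × min(3w, 300).
- Day 2 total, the same under both: D = min(6w, 300).

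The cap starts to bind at 300 / 6 = 50 kg in A and at 300 / 3 = 100 kg in B.

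**Results**

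| Weight (kg) | B: 4.3.1 literal (mg) | A: synopsis and Table 3 (mg) | A / B | D: Day 2 (mg) | B / D |
|---|---|---|---|---|---|
| 10 | 60 | 120 | 2.0 | 60 | 1.0 |
| 20 | 120 | 240 | 2.0 | 120 | 1.0 |
| 40 | 240 | 480 | 2.0 | 240 | 1.0 |
| 50 | 300 | 600 | 2.0 | 300 | 1.0 |
| 60 | 360 | 600 | 1.67 | 300 | 1.2 |
| 75 | 450 | 600 | 1.33 | 300 | 1.5 |
| 100 | 600 | 600 | 1.0 | 300 | 2.0 |

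For example, at 20 kg B = 2 × (3 × 20) = 120 mg and A = 2 × (6 × 20) = 240 mg. At 60 kg B = 2 × 180 = 360 mg and A = 2 × 300 = 600 mg.

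**Which reading the neighbouring text fits**

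1. Section 8.1.8 calls the first 24 hours a loading period. Under B, a child of up to 50 kg receives the same total on Day 1 as on Day 2 (B / D = 1.0), so nothing extra is loaded. Under A, the Day 1 total is twice the Day 2 total at every weight.
2. Section 4.3.2 sets a maximum of 300 mg at each of two Day 1 administrations. Under B, a participant would have to weigh 100 kg to reach it on Day 1; under A, 50 kg.
3. The synopsis and Table 3 agree with each other.

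Four places are therefore consistent with one another, and Section 4.3.1 is the exception. In Table 3 the words about each administration qualify the 300 mg cap. That 6 mg/kg applies to each infusion is inferred from the dosage level together with the BID regimen; it is not stated outright.

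**The case against.** The strongest reply is that this is one loosely chosen unit in a rationale section. Section 4.3 is headed as justification, and Section 4.1 sends the reader to Section 6.1 for doses. The synopsis, Table 3, Section 4.3.2 and Section 8.1.8 all point the same way. Preparation instructions are in the Pharmacy Manual, which is not available here and may be unambiguous. The population PK model uses the dose actually given (Section 9.6.2), which limits the harm to that analysis, and Section 6.4 has injection volumes counted and recorded, so a departure might be noticed.

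Most of this stands. It means that divergent site dosing is a possibility and has not been shown. It does not remove the conflict: the sentence in Section 4.3.1 is worded as an instruction, and Section 8.9.2.2 names Section 4.3 as the place where dosing selection is described.

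Two stronger readings are tempting, and the documents do not support them. A reader might infer that whether a dose counts as an overdose depends on which section is consulted. It does not: Section 8.5 says "an overdose is any dose higher than the protocol-specified dose as provided in Section 6.1", which names one section, and not 4.3.1. A reader might also take the twofold difference to hold for every participant. It holds only up to 50 kg, and the older cohort (12 to <18 years) may include heavier participants.

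**Conclusion.** The inconsistency is real and in current text. Taken literally, Section 4.3.1 gives a Day 1 IV total half that of the synopsis and Table 3 from 10 to 50 kg. The gap closes gradually above 50 kg and disappears at 100 kg. These figures assume that the per-day unit is read as a divided daily total, that the dosage level in the synopsis and Table 3 applies to each infusion, and that the 300 mg cap applies to each infusion.

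The point is an internal inconsistency in a stated pediatric starting dose. No design decision, endpoint or analysis is in question. The documents do not show that any site would dose from Section 4.3.1, so under-treatment or added variation in early exposure remains a risk to be closed off, not a demonstrated effect. No view is taken here on which dose is right; that is for the sponsor to confirm.

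**What to change.** Reconcile Section 4.3.1 with the synopsis, Table 3, Section 4.3.2 and Section 8.1.8, so that all state the Day 1 IV dose in the same unit and say explicitly whether the mg/kg figure applies to each infusion or to the whole day. The sponsor should confirm the intended dose and check that the Pharmacy Manual uses the same wording. The cost is about one sentence in the next amendment or a clarification letter. Sample size, endpoints and analyses are unaffected.
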